7.3 Variables

7.3.1 Exposure

The main exposure of interest in the present study is DL use identified in the national prescription registers by use of Anatomical Therapeutic Chemical Classification System (ATC) code R06AX27. The exploratory analysis will describe DL use based on data about persons who have redeemed at least one DL prescription (Substudy 1). In the association studies (Substudies 2B, 3B, and 4B), DL use is considered a time-varying variable, as the same person can be both exposed and unexposed during the study period depending on the time period from last redeemed DL prescription and the amount of days' supply redeemed at the last DL prescription redemption.

For the association analyses, person time exposed to DL will be determined from dispensing records and period of current use will be defined for each prescription as days' supply starting from the date of redemption plus a 4 week grace period to account for intermittent use and a possible wash-out effect. To minimize exposure misclassification, we propose to use person time at least 26 weeks beyond the dispensing date of the prior prescription as the "unexposed" reference period (in supplementary analysis 7, an alternative period of 52 weeks beyond the prior prescription is used to define the unexposed reference period). If a new DL prescription redemption occurs during an exposed period (either during the period equal to the sum of the days' supply or the 4 week grace period), the exposure period extends from that date with a period equal to the sum of days' supply in the newly redeemed prescription plus a 4 week grace period. In addition, a prescription redemption before 26 weeks after previous prescription redemption would mark the start of a new exposed period (and would not result in an unexposed period). [Figure 1](#) below provides an example of how persons included in the association analyses enter and exit exposure periods during the study period.

Days' supply will be calculated from the quantity of tablets or amount of solution dispensed and the standard daily dose based on the age of the patient (i.e., 6-11 months: 1 mg/day; 12 months-5 years: 1.25 mg/day; 6-11 years: 2.5 mg/day; ≥ 12 years: 5 mg/day).

Figure 1 Example of current exposed periods versus unexposed periods for study subjects included in the association analyses (Substudies 2B, 3B, and 4B).

[figure not shown]

Figure 1 illustrates how subjects in the study population (i.e., restricted to persons with at least one redeemed prescription of DL) enter and exit exposed and unexposed periods. An exposed period is a period starting from the day of redemption of a DL prescription and includes the following period equal to the number of days' supply in the drug packages purchased (illustrated with dark grey boxes) and a 4-week grace period (illustrated with the light grey boxes). Unexposed periods, which start 26 weeks after the dispensing date of the last DL prescription, are depicted with white boxes. The time between the end of the exposed period and the unexposed period is considered neither exposed nor unexposed; these periods are illustrated with shaded boxes. Moreover, the date at which an outcome (i.e., seizure, SVT, or A-fib/flu) occurs (if occurring) is marked with a black triangle. For example, person 1 experienced the outcome before redeeming DL for the first time (date of entering the study); and therefore, this person will be excluded. Person 2 experienced the first outcome while in an exposed period and a recurrent outcome occurred in an unexposed period. Person 3 was exposed to DL twice, but did not experience an outcome. Finally, person 4 was exposed to DL once and experienced the outcome in a period where the person was neither exposed nor unexposed; therefore, this outcome will not count toward the analysis of the association.

In a supplementary analysis, an individual's exposure status is categorized according to time since last DL dispensing (periods 0–4, 5–8, 9–16, and 17–26 weeks each compared with >26 week since last DL dispensing), and individuals are considered unexposed in the period beyond 26 weeks after a DL prescription redemption until next DL prescription redemption, the end of the study period, death, emigration, or occurrence of the outcome, whichever comes first.

Loratadine, the parent compound of DL, is also available via prescription and over-the-counter in the Nordic countries. We think it is somewhat unlikely that patients would switch between DL and loratadine; however, it is possible that some of the time counted as unexposed in the analyses could actually be time exposed to loratadine. Moreover, other non-sedating prescription antihistamines are available in the Nordic countries, and if the effect on the outcomes is driven by use of non-sedating antihistamines in general rather than the specific effect of DL exposure, these drugs should be examined to elucidate potential misclassification of exposure. To explore exposure misclassification (i.e., the influence of loratadine and other non-sedating prescription antihistamines), on the associations under study), we will conduct supplementary analyses, which will be specified in the statistical analysis plan.

Regarding missing values in variables from the prescription registers, normally no registration is interpreted as the person does not use the drug (e.g., no registration of DL use is interpreted as the person has not used DL). Prescription drugs are not available from sources other than the pharmacies, and all drugs purchased at pharmacies are included in the prescription register (the only exception are drugs supplied from hospitals, however less than 1% of DL is supplied by the hospitals). We do not expect missing information for data in the prescription registry that will be used to determine DL exposure (e.g., number of packs per redemption). However, we will examine data to see whether missing information occurs. Missing data handling will be determined after review of the data, but before data from different registers are linked together (e.g. handling of missing values for exposure data is blinded to outcome status and vice versa) and will be described in a data control report, which will be submitted with the study report.

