Pharmacoepidemiological studies typically use dispensed days' supply as a surrogate for current drug exposure, assuming they are used every day. However, in contrast to medications for many chronic diseases, antihistamines may be used intermittently, as needed for symptoms. For the main analyses in the present study of the association between current DL use and outcomes of interest (Substudies 2B, 3B, and 4B), person time exposed to DL will be determined from dispensing records. "Current use" (i.e., "exposed" period) will be defined for each prescription as the sum of days' supply plus a 4 week grace period to account for intermittent use and a possible wash-out effect. If a new DL prescription redemption occurs during an exposed period (either during the period equal to the sum of the days' supply or the 4 week grace period), the exposure period extends from that date with a period equal to the sum of days' supply in the newly redeemed prescription plus a 4 week grace period. Note: Days' supply will be calculated from the quantity of tablets or amount of solution dispensed and the standard daily dose based on the age of the patient (i.e., 6-11 months: 1 mg/day; 12 months-5 years: 1.25 mg/day; 6-11 years: 2.5 mg/day; ≥ 12 years: 5 mg/day). Because the drug is used "as needed", it is quite possible that there may still be exposed days in the period after the latest exposed period (i.e., after the exposed period that includes the sum of the days' supply plus a 4 week grace period). To minimize exposure misclassification, we propose to use person time at least 26 weeks beyond the dispensing date of the prior prescription as the "unexposed" reference period. The "unexposed" period is actually a period with remote exposure to DL because dispensing of DL is a condition of entering the study population. We will refer to the "remote exposure" period as "unexposed" (For more details, see section 7.3.1 and [Figure 1](#)). The time between the exposed period and the unexposed period is considered neither exposed nor unexposed.

The advantage of using this design restricted to DL users, in which the same persons may have both exposed and unexposed periods, is that we reduce confounding due to time-independent factors associated with DL use.

The study is divided into six parts described below (For more details, see section 7.7).

1. Substudy 1

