A cohort study among ever-DL users analyzing the association between exposed and unexposed time and first seizures will be performed for the total population and stratified by age. Current use (i.e., “exposed” period) will be defined for each prescription as days’ supply plus a 4 week grace period to account for intermittent use and a possible wash-out effect. Unexposed time will be defined as the period starting 26 weeks from the dispensing date of the prior DL prescription until the next DL prescription redemption, if any. A person who has redeemed at least one prescription of DL is included in the cohort and enters the cohort at the date of first prescription redemption. Study individuals are followed until occurrence of a seizure; occurrence of one of the conditions described in section 7.2.2; 31 December 2015; emigration; or death, whichever comes first. The association between exposure to DL and first seizure will be evaluated using Poisson regression of the IR of first seizure, and the measure of effect is the IRR. A person with prescription redemption of DL in Norway and Sweden within the first 6 months after establishment of the prescriptions registers will not be included in order to account for truncation bias. In addition we exclude persons with DL prescription redemptions within 6 months after immigrating to Denmark, Finland, Norway, or Sweden. The analyses will be adjusted for confounders identified from the DAG (i.e., country, age, sex, calendar year, seasonality, severity of rhinitis, asthmatic status, and chronic urticaria status) (Table 4). We will evaluate whether age can be included as a continuous variable by examining the assumption of linearity. Alternatively, age will be included as a categorical variable.

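### Read literally, the refill rule lets a small early redemption shorten the exposed period; it conflicts with the per-prescription definition, and the 26-week reference clock ignores supply

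*Protocol*

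**What the plan says.** Three statements in the Protocol bear on what happens when a person redeems DL again while still exposed.

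- **Refill rule (7.1 and 7.3.1).** Section 7.3.1: "the exposure period extends from that date with a period equal to the sum of days' supply in the newly redeemed prescription plus a 4" (weeks of grace). Section 7.1 has the same rule. No term carries forward supply left from the earlier dispensing. Section 7.3.1 also makes exposure status depend on the time since the last redemption and on "the amount of days' supply redeemed at the last DL prescription redemption".
- **Per-prescription definition (7.3.1).** "period of current use will be defined for each prescription as days' supply starting from the date of redemption plus a 4 week grace period". On this wording each prescription has its own window.
- **Reference time (7.3.1 and 7.7.2).** "Unexposed time will be defined as the period starting 26 weeks from the dispensing date of the prior DL prescription". The text under Figure 1 agrees and adds: "The time between the end of the exposed period and the unexposed period is considered neither exposed nor unexposed". An event in that gap does not count in the association analysis.

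The Protocol does not say what happens when the new prescription contains less than the supply still in hand.

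**The concern.** Under the literal refill rule the end of exposure is set by the newest redemption alone. A person who collects a small pack while holding a large one would then leave the exposed category earlier than a person who collected nothing more. Current use would not increase steadily with the amount dispensed. The time lost, and any seizure, supraventricular tachycardia or atrial fibrillation/flutter in it, would drop out of the main analyses in Substudies 2B, 3B and 4B.

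The per-prescription wording leads to a different end date for the same records, so two programmers could code the primary exposure differently and both claim to follow the Protocol.

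A second, separate weakness is that reference time starts a fixed 26 weeks after the last dispensing, however much was dispensed.

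**Working it through.** **The Protocol's own figure.** Section 7.5.2 is the only place that combines supply over several prescriptions: exposed weeks = mean prescriptions per year × 4 + 4. This reproduces for all four age groups: 1.50 × 4 + 4 = 10.00; 1.62 × 4 + 4 = 10.48; 1.78 × 4 + 4 = 11.12; 2.30 × 4 + 4 = 13.20. It adds all supplies and applies one grace period. The Protocol calls it a simplified planning method, so it does not settle the analysis rule.

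**Inputs.** Grace period 28 days (4 weeks). Reference clock 26 × 7 = 182 days. Planning supply 28 days per prescription. The Protocol gives no pack sizes, so every other supply below is an assumption.

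**Formulas.** First supply S1 on day 0, refill of S2 on day r, leftover L = S1 − r (zero if negative).

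- Restart reading (literal rule): exposure ends at r + S2 + 28.
- Union reading (each prescription keeps its window): exposure ends at the later of S1 + 28 and r + S2 + 28.
- With an early refill, supply in hand ends at r + L + S2.
- Reference starts at r + 182.

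**Conditions that follow.**

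1. The refill shortens exposure when r + S2 + 28 < S1 + 28, that is when S2 < L, and only on the restart reading. An equal-size refill never does.
2. On the restart reading, supplied time leaves the exposed category when L exceeds 28 days, by L − 28 days.
3. Supplied time falls in the reference when L + S2 exceeds 182 days, by L + S2 − 182 days.

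| S1, r, S2 (days) | L | Restart end | Union end | Supply end | Reference start | Supplied days not exposed (restart / union) | Supplied days in reference |
|---|---|---|---|---|---|---|---|
| 28, 7, 28 | 21 | 63 | 63 | 56 | 189 | 0 / 0 | 0 |
| 60, 10, 60 | 50 | 98 | 98 | 120 | 192 | 22 / 22 | 0 |
| 98, 10, 30 | 88 | 68 | 126 | 128 | 192 | 60 / 2 | 0 |
| 100, 10, 100 | 90 | 138 | 138 | 200 | 192 | 62 / 62 | 8 |
| 200, 10, 30 | 190 | 68 | 228 | 230 | 192 | 162 / 2 | 38 |

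In the 98-then-30 case the refill ends exposure 126 − 68 = 58 days early on the restart reading. Days 68 to 126 lie before the reference starts on day 192, so they count as neither.

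At the planning supply of 28 days, a single early refill leaves at most 27 days over. The 28-day grace covers this and no supplied time is lost on either reading.

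In the last row the union end (day 228) falls after the reference start (day 192), so 36 days would be both exposed and unexposed. The same overlap arises with no refill when one dispensing exceeds 182 − 28 = 154 days' supply.

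**The case against.** The strongest reply is that the rule says exposure extends, and that current use is defined prescription by prescription. On that union reading the 98-day window runs to day 126 and the refill shortens nothing. This is a fair reading, but the sentence tying status to the last redemption points the other way and the Protocol does not choose. The ambiguity stands.

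Several further objections succeed and limit the point:

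- A reader might infer that the refill pushes supplied time into the reference. It does not: a refill always postpones the reference start, to r + 182. Supplied time reaches the reference only because the clock ignores supply.
- A reader might count supply plus grace as misassigned. For two 100-day packs on days 0 and 10 that gives 228 − 192 = 36 days, but 28 are grace and only 8 are supplied. For three such packs on days 0, 10 and 20 it gives 328 − 202 = 126 days, of which 98 are supplied.
- A reader might infer dilution of the IRR toward 1. Time moved to neither is dropped with its events; this costs information but does not contaminate the reference. Only supplied time placed in the reference would tend to pull the IRR toward 1.
- Carry-over of unused supply is not clearly better. Section 7.7.5 notes that dosing for chronic urticaria is typically a multiple of the standard dose. For such users an early refill may mean that the earlier supply is used up.

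Supplementary analyses bear on this but do not repair the main analysis. Analysis 7 (52 weeks) moves the reference past supply plus grace in the 98-then-30 and 100-day examples, but restores no exposed time. Analysis 3, on one reading, removes such persons as high-dose users (98 days' supply redeemed 10 days before the next fill is about ten times the interval). Analysis 1 resets at each refill.

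**Conclusion.** The point holds as an unresolved conflict within sections 7.1 and 7.3.1, one reading of which gives a perverse result: a refill smaller than the leftover supply ends exposure early. In the assumed 98-then-30 example the loss is 58 days. This is wording the Protocol fixes itself, not detail left to a later plan.

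The reference-clock weakness is separate and an edge case. It needs leftover plus new supply above 182 days and yields 8 supplied days for two 100-day packs 10 days apart.

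The size in the study is unknown. The Protocol gives neither supply distributions nor refill intervals, so frequency and net effect on the IRR cannot be computed. Planning figures of 4 weeks' supply and 1.50 to 2.30 prescriptions a year suggest that the effect may be small. The wording should still be corrected, because it defines the primary exposure and the remedy is cheap.

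**What to change.** In sections 7.1 and 7.3.1, state that:

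1. after a redemption during an exposed period, exposure ends at the later of (i) the existing end date and (ii) the redemption date + new days' supply + 4 weeks;
2. reference time starts at the later of 26 weeks after the last dispensing and the end of the exposed period. Align section 7.7.2 with this.

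The first sentence means that a refill can never shorten exposure. The second prevents time from being both exposed and unexposed. They do not remove every supplied day from the reference: for two 100-day packs on days 0 and 10, exposure still ends on day 138 and the reference still starts on day 192, so the 8 supplied days remain. Only carry-over of unused supply would remove them. It should be at most a sensitivity analysis, because it can overstate duration in higher-dose users.

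The cost is two sentences and a small programming change on dispensing data already held. Section 5 says the methods differ from the earlier three-country study (P203) only by removal of the secondary analyses. If P203 was programmed on the restart reading, report both versions so that the results stay comparable.

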7.3.2 Outcomes

Three outcome variables will be used in the present study: first seizure (Substudy 2B), first SVT (Substudy 3B), and first A-fib/flu (Substudy 4B). Except where noted, the case definition of seizure excludes febrile seizure, a condition in infancy and early childhood attributed to fever. However, supplementary analysis 2 will evaluate the outcomes of febrile and non-febrile seizures in children. (The diagnosis of febrile seizure is generally not used in adults.) Information on outcome variables will be obtained from the Nordic national patient registers, including diagnostic and treatment information for patients treated at the secondary and tertiary hospital level in all four Nordic countries using International Classification of Diseases (ICD)- 10 codes. We will exclude seizure cases if they are registered with brain tumor (benign and malignant), stroke, or acute drug intoxication or overdose of drugs during the same hospitalization as the seizure. [Table 2](#) gives an overview of the outcome variables in the study. For all outcome variables, we will include the primary diagnoses from the emergency room or inpatient settings registered in the Nordic national patient registers.

The National Patient Registers are used for reimbursement of services to the hospitals. It is mandatory to enter specific information (such as name, date, main diagnosis) for the record to be established. Due to the requirements of the national registries, we do not expect missing data on the outcome variables. In Denmark and Finland, it is only possible to register hospitalizations into the Nordic national patient registers if complete information on the primary diagnosis, date, and hospital department is entered into the registration system. Therefore, no missing values should occur for these variables. This procedure is most likely the same for Sweden and Norway. Data in the Danish National Patient Register is automatically checked for missing codes, inconsistencies between diagnosis and gender, incorrect digits and errors in the personal identification code (PIC). If an error is detected, the record is returned to the source hospital for correction [Schmidt, M., et al 2015]. No studies have examined the validity of seizures in the total population, but Vestergaard et al (2006) examined the validity of the discharge diagnosis of febrile seizure in children the National Patient Register (ICD-10 code R56.0) [Vestergaard, M., et al 2006]. The positive predictive value (PPV) was 92.8% (95%CI: 88.8-95.7%). The sensitivity (defined as completeness by the authors) is 71.5% (95% CI: 66.3-76.4%) [Vestergaard, M., et al 2006]. The diagnosis of atrial fibrillation and atrial flutter has been validated in the Danish National Patient Register [Rix, T. A., et al 2012]. The PPV for the combined diagnosis of atrial fibrillation and atrial flutter (I48) was 92.6%. Other studies have found even higher PPVs [Frost, L., et al 2007] [Frost, L. 2004]. No studies have validated the diagnosis for supraventricular tachycardia (I47); however, we find it likely that this diagnosis has approximately the same validity in the National Patient Register as seen for atrial fibrillation and atrial flutter.

Table 2 Overview of the Outcome Variables in the Study

Substudy	Aim
Substudy 2B	First seizure: An incident case of seizure is a person with the first diagnosis of seizure
Substudy 3B	Supraventricular tachycardia (SVT): An incident case of SVT is a person with first diagnosis of SVT
Substudy 4B	Atrial fibrillation or atrial flutter (A-fib/flu): An incident case of A-fib/flu is a person with first diagnosis of A-fib or first diagnosis of A-flu. These two diagnoses will be combined into a composite endpoint

ICD-10 codes are listed in Annex 6. Note that the case definition of seizure in these substudies excludes febrile seizures.

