12.6 Annex 6 ICD-10 Codes and ATC Codes

Diagnosis/drugs to be identified in registers	Proposed classification system	Proposed codes by clinicians
Acute drug intoxication and overdose of drugs	ICD-10	T88.6 T88.7 T36 T50
Antiepileptic medicine	ATC	N03A N05BA
Asthma	ICD-10	J45
	ATC	R03A and R03B
Atrial fibrillation or flutter	ICD-10	I48
Brain Tumor (both malignant and benign)	ICD-10	C70 and C71 D33
Chronic urticaria	ICD-10	L50 (excluding acute urticaria: L50.8D) L56.3
Congenital pre-excitation syndrome	ICD-10	I45.6
Desloratadine	ATC	R06AX27
Epilepsy	ICD-10	G40
Head trauma	ICD-10	S06
Loratadine	ATC	R06AX13
Malignant brain tumor	ICD-10	C70 and C71
Seizure	ICD-10	R56
Severe rhinitis (immunotherapy)	ATC	V01AA (excluding V01AA07)
Stroke (all types)	ICD-10	I61 I62 I63 I64.9
Supraventricular arrhythmias	ICD-10	I47.1

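### Annex 6 codes seizure as the whole of R56, although Section 7.3.2 excludes febrile seizures and itself codes them R56.0

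*Protocol*

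**What the plan says.** - **Case definition.** Section 7.3.2 states: "Except where noted, the case definition of seizure excludes febrile seizure, a condition in infancy and early childhood attributed to fever". The exception it notes is supplementary analysis 2, which Section 7.7.5 describes as separating febrile from non-febrile seizures in Substudy 2B at 0–4 years.
- **Pointer to the codes.** The note to Table 2 reads: "ICD-10 codes are listed in Annex 6. Note that the case definition of seizure in these substudies excludes febrile seizures".
- **Febrile code.** On register validity, Section 7.3.2 cites work on the "discharge diagnosis of febrile seizure in children the National Patient Register (ICD-10 code R56.0".
- **Code list.** Annex 6 gives "Seizure ICD-10 R56" and nothing more for seizure. It does write sub-code exclusions elsewhere: "L50 (excluding acute urticaria: L50.8D" for chronic urticaria and "V01AA (excluding V01AA07" for immunotherapy. There is no row for febrile seizure.
- **Other uses of the term.** Section 7.2.2 excludes people with an earlier seizure diagnosis from 2A and 2B. Section 7.7.2 ends follow-up in 2B when a seizure occurs. Neither says whether a febrile seizure counts.

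**The concern.** R56.0 lies inside R56, so the list counts events that the case definition rules out. The missing exclusion cannot be read as the annex's usual shorthand, because the annex spells out exclusions for two other entries.

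Three uses of the code are affected. The 2A rates and the 2B rate ratios could include febrile events, chiefly at 0–4 years. Children with an earlier febrile seizure would be removed at entry if R56 is also used for history. A febrile seizure during follow-up would end it. Dropping R56.0 from the outcome alone settles only the first of these.

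For a safety study the main statistical risk is dilution: if desloratadine were associated with non-febrile but not with febrile seizures, mixing the two would pull the 0–4 year estimate towards 1. Section 5 cites clinical observations of seizures in four children, so this is a stratum in which a signal matters.

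**Working it through.** **1. The plan's own figure.** Inputs for 0–4 years (Section 7.5.6, Annex 7): n = 20,000; E = 10/52 = 0.1923; t = 2 years; background rate 65 per 100,000; one-sided α = 0.05; power 80%.

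p2 = 1 − exp(−0.00065 × 2) = 0.001299. The Annex 7 formula is (p1 − p2)² = (Zα + Zβ)² [p1q1/(En) + p2q2/((1 − E)n)]. Solved for λ = p1/p2, it gives 3.00, as stated. The other seizure rows of Table 6 give 1.45, 1.30 and 1.68 against the stated 1.5, 1.3 and 1.7.

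**2. Expected non-febrile events.** Persons × years × rate, at the Section 7.5 inputs:
- 0–4: 20,000 × 2 × 65/100,000 = 26
- 5–19: 86,000 × 6 × 50/100,000 = 258
- 20–64: 215,000 × 6 × 40/100,000 = 516
- ≥65: 44,500 × 6 × 40/100,000 = 106.8
- Total: 906.8

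This treats 65 per 100,000 as a non-febrile rate. Section 5 describes the cited source's rate as one of unprovoked seizures, which supports that reading.

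**3. Range for the missing febrile rate.** Let the febrile rate at 0–4 be m × 65, with febrile events only in that age group and all of R56 counted.
- Febrile share at 0–4 = m/(1 + m). It passes one half when m > 1, that is, above 65 per 100,000 person-years.
- Mixed IRR, if the true IRR is 3.0 for non-febrile and 1.0 for febrile seizures = (3 + m)/(1 + m).
- Nominal minimum detectable IRR: the Annex 7 formula with rate 65(1 + m).
- Febrile share of the all-ages outcome = 26m/(906.8 + 26m).

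| m (assumed) | Febrile rate per 100,000 | Febrile share, 0–4 | Mixed IRR | Nominal minimum detectable IRR | Febrile share, all ages |
|---|---|---|---|---|---|
| 0.5 | 32.5 | 33% | 2.33 | 2.50 | 1.4% |
| 1 | 65 | 50% | 2.00 | 2.23 | 2.8% |
| 2 | 130 | 67% | 1.67 | 1.95 | 5.4% |
| 5 | 325 | 83% | 1.33 | 1.62 | 12.5% |
| 10 | 650 | 91% | 1.18 | 1.43 | 22.3% |

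In every row the mixed IRR lies below the minimum detectable IRR for the mixed outcome. Under these assumptions the extra events do not make up for the dilution.

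**4. After the correction.** With R56.0 removed, the 0–4 inputs are those of step 1 and the result stays at 3.00. That depends on 65 being non-febrile. If a quarter or a half of it were febrile, the non-febrile rate would be 48.75 or 32.5 and the result 3.47 or 4.37.

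**The case against.** The text already resolves the conflict: the exclusion is stated twice, the second time directly after the pointer to Annex 6. A programmer who follows it would drop R56.0. The annex describes its entries as codes proposed by clinicians for diagnoses to be found in the registers, and the whole of R56 has to be extracted because supplementary analysis 2 needs the febrile cases. Under Section 7.6 the Danish coordinator joins the national datasets and derives variables, and under Section 7.8 two researchers program independently. This lowers the risk, and differences between countries are only a possibility. It does not make the list right, and it does not settle prior history or the end of follow-up.

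Several stronger readings are tempting and are not supported:
- **That the 0–4 result would be mostly febrile.** This needs a rate the protocol does not give, and it assumes the list overrides the text.
- **That febrile events would dominate the pooled seizure result.** On the step 2 counts this needs m > 906.8/26 = 34.9, a febrile rate of about 2,267 per 100,000 person-years. Section 7.3.2 says the febrile diagnosis is generally not used in adults, so the adult strata are essentially untouched.
- **That infection would confound the estimate without any control.** The seizure DAG links infections to desloratadine only through chronic urticaria, which is in the primary adjustment set, and supplementary analysis 8 adds infections.
- **That excluding children with an earlier febrile seizure is an error.** Section 7.2.2 also gives high risk from other causes as a reason for exclusion, so this is a choice the protocol has to make and state.

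**Conclusion.** The inconsistency stands: the code list and the case definition cannot both be applied. If the list were applied as written, the 2A and 2B seizure outcome would be contaminated by febrile seizures, mainly at 0–4 years, and a non-febrile association there would be diluted. The size cannot be computed from the protocol. What can be said is that febrile events become the majority at 0–4 once their rate passes 65 per 100,000 person-years, and that at equal rates an IRR of 3.0 would read as 2.0. Both statements take 65 as a non-febrile rate, and the second also takes a febrile IRR of 1.0.

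No stated sample-size figure is wrong because of this. An SAP, which is not at hand, may give the codes in full, but that would not bring the protocol's own definition and annex into agreement. The correction should be made before the outcome is programmed.

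**What to change.** In Annex 6:
- Replace the seizure row with *Seizure (primary outcome): R56 excluding R56.0*.
- Add a row *Febrile seizure (supplementary analysis 2): R56.0*.

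In Sections 7.2.2 and 7.7.2, state whether R56.0 counts as a prior seizure diagnosis at entry and whether it ends follow-up, with the same rule in all four countries.

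The cost is a few lines of text and the matching program code, with no new data. There will be fewer events at 0–4 years than under the whole of R56, as the text already intends. The minimum detectable IRR of 3.0 needs no change, provided the 65 per 100,000 is confirmed as a non-febrile rate.
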